## Adverse Events

Adverse events (with the exception of disease progression) will be reported by the subject (or, when appropriate, by a caregiver, surrogate, or the subject's legally acceptable representative) or by the medical staff from the time of the signed and dated ICF until 30 days following the last dose of any study drug. Adverse events will be followed by the investigator as specified in Section 12, Adverse Event Reporting.

## Clinical Laboratory Tests

Blood samples for serum chemistry and hematology will be collected. The investigator must review the laboratory report, document this review, and record any clinically relevant changes occurring during the study in the adverse event section of the eCRF. The laboratory reports must be filed with the source documents. The analysis of bone marrow samples will be performed locally and evaluated by the investigator.

The following tests will be performed by the local laboratory unless otherwise indicated:

- Hematology Panel
  - Hemoglobin
  - platelet count
  - white blood cell (WBC) count
  - absolute neutrophil count (ANC)
  - peripheral blast count
- Serum Chemistry Panel
  - Sodium
  - Potassium
  - Creatinine
  - aspartate aminotransferase (AST)
  - alanine aminotransferase (ALT)
  - total bilirubin
  - serum uric acid
- Urine or serum pregnancy testing for females of childbearing potential at screening is required and during the study when clinically indicated.

**Vital Signs:** (pulse, temperature, and blood pressure) will be performed at screening and as needed during the study.

**Physical Examination:** A complete physical examination will be performed during the Screening Phase. Thereafter, only a symptom directed physical examination is required. Abnormalities will be recorded in the appropriate section of the eCRF.

**Karnofsky/Lansky Performance Status Score:** Karnofsky/Lansky Performance Status (see) will be used to evaluate the effect of the disease status on the activities of daily living, and will be performed at the times specified in the Time and Events Schedule.

**Lansky Performance Status:**

Rating	Description
100	fully active, normal
90	minor restrictions with strenuous physical activity
80	active, but gets tired more quickly
70	both greater restriction of, and less time spent in, active play
60	up and around, but minimal active play; keeps busy with quieter activities
50	lying around much of the day, but gets dressed; no active play; participates in all quiet play and activities
40	mostly in bed; participates in quiet activities
30	stuck in bed; needs help even for quiet play
20	often sleeping; play is entirely limited to very passive activities
10	does not play nor get out of bed
0	unresponsive

**Karnofsky/ Performance Status:**

Condition	Performance status %	Comments
Able to carry on normal activity and to work. No special care needed.	100	Normal. No complaints. No evidence of disease.
	90	Able to carry on normal activity. Minor signs or symptoms of disease.
	80	Normal activity with effort. Some signs or symptoms of disease.
Unable to work. Able to live at home and care for most personal needs. A varying degree of assistance is needed.	70	Cares for self. Unable to carry on normal activity or to do active work.
	60	Requires occasional assistance, but is able to care for most of personal needs.
	50	Requires considerable assistance and frequent medical care.
Unable to care for self. Requires equivalent of institutional or hospital care. Disease may be progressing rapidly.	40	Disabled. Requires special care and assistance.
	30	Severely disabled. Hospital admission is indicated although death is not imminent.
	20	Hospitalization necessary. Very sick, active supportive treatment necessary.
	10	Moribund; fatal processes progressing rapidly.
	0	Dead.

**9.6. Sample Collection and Handling**

The actual dates and times of sample collection must be recorded in the laboratory requisition form. If blood samples are collected via an indwelling cannula, an appropriate amount (1 mL) of serosanguineous fluid slightly greater than the dead space volume of the lock will be removed from the cannula and discarded before each blood sample is taken. After blood sample collection, the cannula will be flushed with 0.9% sodium chloride, United States Pharmacopeia (USP) (or equivalent) or sodium heparin of 10 U/mL as per local practice and charged with a volume equal to the dead space volume of the lock. If a mandarin (obturator) is used, blood loss due to discard is not expected.

Refer to the Time and Events Schedule for the timing and frequency of all sample collections.

Instructions for the collection, handling, storage, and shipment of samples are found in the laboratory manual that will be provided. Collection, handling, storage, and shipment of

samples must be under the specified, and where applicable, controlled temperature conditions as indicated in the laboratory manual.

Any volume of blood collected must be consistent the recommendations of the European Medicines Agency (EMA) for study related blood loss. In pediatric populations this should be no more than 3% of the total blood volume during a four week period and not more than 1% of total blood volume at a single time point. At a total blood volume estimated at 80 to 90 mL/kg body weight this equals 2.4 to 2.7 mL of blood per kilogram of body weight every four weeks or 0.8 to 0.9 mL per kilogram at any one time.

It is the responsibility of the investigator to comply with these guidelines and to prioritize study blood collection as follows:

1. Safety laboratory studies (hematology and serum chemistry) that are trial related and not part of routine care
2. Pharmacokinetic samples
3. Samples for DNA methylation and DNA mutation.
4. Samples for gene expression profiling and microRNA analysis.

## **10. SUBJECT COMPLETION/WITHDRAWAL**

### **10.1. Completion**

A subject will be considered to have completed the study if he or she has completed the follow-up phase, has died before the end of the study, has been lost to follow up, or has withdrawn consent for study participation before the end of the study.

### **10.2. Discontinuation of Study Treatment (Sequential DACOGEN - cytarabine)**

If a subject's study treatment must be discontinued, the End of Sequential Treatment Visit should be performed however, this will not result in automatic withdrawal of the subject from the study. The subject may, at the discretion of the investigator, receive single agent DACOGEN in the Continuation Phase (see Section 9.1.5), otherwise the subject will enter the Follow-up Phase of the study. The End of Sequential Treatment/End of Treatment Visit and Follow-up visit assessments should be performed as specified in the Time and Events Schedule.

A subject's study treatment should be discontinued if:

- The subject experiences a DLT in the Phase 1 portion of the study
- The investigator believes that for safety reasons (eg, adverse event) it is in the best interest of the subject to discontinue study treatment
- The subject becomes pregnant
- The subject has progressive disease by IWG criteria
- The subject is non-compliant with regard to treatment visits
- The subject has sufficient clinical response, in the opinion of the investigator, to be eligible for transplant

- The subject starts another treatment regimen for AML
- The subject is unable to adhere to the study visit schedule or comply with protocol requirements
- The subject or subject's legal representative, parent, or guardian withdraws consent/assent for study treatment.

### **10.3. Withdrawal from the Study**

A subject will be withdrawn from the study for any of the following reasons:

- Lost to follow-up
- Withdrawal of consent/assent by the subject or the subject's legal representative, parent, or guardian.
- Sponsor terminates the study

If a subject is lost to follow-up, every reasonable effort must be made by the study site personnel to contact the subject and determine the reason for discontinuation/withdrawal. The measures taken to follow up must be documented.

When a subject withdraws before completing the study, the reason for withdrawal is to be documented in the eCRF and in the source document. Study drug assigned to the withdrawn subject may not be assigned to another subject.

If a subject withdraws from the study the research samples will be destroyed and no further testing will take place. To initiate the sample destruction process, the investigator must notify the sponsor study site contact of withdrawal of consent/assent for the research samples and to request sample destruction. The sponsor study site contact will, in turn, contact the biomarker representative to execute sample destruction. If requested, the investigator will receive written confirmation from the sponsor that the samples have been destroyed.

## **11. STATISTICAL METHODS**

Statistical analysis will be done by the sponsor or under the authority of the sponsor. A general description of the statistical methods to be used to analyze the efficacy and safety data is outlined below. Specific details will be provided in the Statistical Analysis Plan.

### **11.1. Subject Information**

The safety population includes subjects who have signed the ICF and have received at least 1 dose of any study drug. The efficacy population is the subset of the safety population consisting subjects who are evaluable for disease response. Where appropriate, summaries (demographic, baseline characteristics, efficacy, and safety) will be presented for Phase 1 part of the data, Phase 2 part of the data, and data of the 2 phases combined.

### **11.2. Sample Size Determination**

The Phase 1 portion of the study will enroll up to 12 evaluable subjects (18 if the intermediate cytarabine dose is used), depending on when the MTD is determined. The Phase 2 portion of the study will enroll at least 15 evaluable subjects including those who received the MTD of cytarabine for up to 4 cycles in Phase 1 portion of the study and are evaluable.

The estimated numbers of subjects are 15 (20 if the interim dose is tested) for Phase 1, and 17 for Phase 2 (including those who received the MTD of cytarabine in Phase 1) allowing for those who are not evaluable.

### 11.3. Phase 1 Analysis

Subjects in the Phase 1 portion will be assessed for toxicity (DLT) to determine the recommended dose of cytarabine for the Phase 2 study.

### 11.4. Efficacy Analyses

#### Criteria

##### *Primary Endpoint*

The primary efficacy endpoint is the response rate of CR + CRi for evaluable subjects from the Phase 2 part of the study. The best response observed at any time point during the first 4 cycles of study treatment will be used.

Best response of CR + CRi for subjects from the Phase 1 part of the study, and from Phase 1 and Phase 2 parts combined will also be summarized.

The aim of the statistical analysis of the initial efficacy data is to assist decision making for further clinical development of DACOGEN sequential therapy. Such a decision will be in consultation with regulatory authorities, and will depend primarily on the totality of the data from this and other studies, available treatment options for pediatric AML patients at the time, and interest of co-operative study groups.

The sequential therapy is considered not to have a clinically interesting activity if the underlying response rate (CR + CRi) is  $\leq 20\%$ , and is considered to have a clinically interesting activity if the underlying response rate is  $\geq 35\%$ . Because of the small sample size (15 subjects), only descriptive statistics, ie, the observed response rate of CR + CRi and the 95% confidence interval (CI), will be provided without any hypothesis testing. Also, due to the small sample size, the observed response rate will have much variability. With these considerations, descriptive statistical analyses will focus on 2 assessments that are considered adequate and reasonable in the context of small sample sizes.

The first analysis is to use the lower boundary of the 95% CI to assess if an underlying response rate that is much smaller than 20% can be ruled out. For instance ([Table 5](#)), with a total of 15 subjects, to rule out an underlying response rate of 5%, there should be at least 4 responders, and to rule out an underlying response rate of 3%, there should be at least 3 responders.

The second statistical assessment to assist in decision making is the “false positive” and “false negative” error rates. This assessment estimates the probability of chance findings with the given sample size. Suppose a “yes” or “no” answer is sought in terms of whether the outcome, say  $x$  CR + CRi responders out of the 15 subjects, favors a continuation of the clinical program. The “false positive” error rate for a “yes” answer is the probability of observing  $\geq x$  responders when the underlying response rate is 20%; and the “false negative” error for a “no” answer is the probability of observing  $\leq x$  responders when the underlying

response rate is 35%. Table 5 illustrates the false positive and false negative error rates depending on the number of responders. For instance, if only 2 or 3 subjects have responded, the “false positive” error rate for a “yes” answer is very high (83% or 60%) indicating a “yes” is likely an incorrect answer, while the “false negative” error rate for a “no” answer is low (6% or 17%) indicating a “no” is likely a correct answer.

**Table 5: Statistical Assessments of Response of CR + CRi (N=15)**

Number of Responders	Response Rate (%)	Exact 95% CI (%) a	False Positive Error (%) b	False Negative Error (%) c
1	6.7	(0.2, 31.9)	96.5	1.4
2	13.3	(1.7, 40.5)	83.3	6.2
3	20.0	(4.3, 48.1)	60.2	17.3
4	26.7	(7.8, 55.1)	35.2	35.2
5	33.3	(11.8, 61.6)	16.4	56.4
6	40.0	(16.3, 67.7)	6.1	75.5
7	46.7	(21.3, 73.4)	1.8	88.7

a Based on Clopper-Pearson Exact Interval

b Probability of observing this or greater number of responders if the underlying response rate is 20%.

c Probability of observing this or fewer number of responders if the underlying response rate is 35%.

### **Major Secondary Endpoints**

Duration of CR + CRi, overall response (CR + CRi + PR) rate, event-free survival, and overall survival will be summarized. These summaries are also based on data of the Phase 2 part of the study. Where appropriate, these summaries will be performed on data from the Phase 1 part of the study and Phase 1 and Phase 2 parts combined. The start time for EFS and OS determination is the date of the first dose of study drug.

### **11.5. Pharmacokinetic Analyses**

Population PK analysis of plasma concentration-time data of decitabine will be performed using nonlinear mixed-effects modeling. Data may be combined with those of other selected studies to support a relevant structural model. Available baseline subject characteristics (demographics, laboratory variables, genotypes, race, etc.) will be tested as potential covariates affecting PK parameters. Details will be given in a population PK analysis plan and the results of the population PK analysis will be presented in a separate report.

A snapshot date for PK samples to be analyzed will be defined, if required. Samples collected before this date will be analyzed for decitabine and included in the population PK analysis. Samples collected after the snapshot date will be analyzed at a later date, and may be included in a population PK re-analysis when they become available after database lock.

Data will be listed for all subjects with available plasma concentrations per treatment group. Subjects will be excluded from the PK analysis if their data do not allow for accurate assessment of the PK (eg, incomplete administration of the study drug; missing information of dosing and sampling times; concentration data not sufficient for PK parameter calculation).

All concentrations below the lowest quantifiable concentration or missing data will be labeled as such in the concentration database. All subjects and samples excluded from the analysis will be clearly documented in the study report.

For each treatment group, descriptive statistics, including arithmetic mean, SD, coefficient of variation, median, minimum, and maximum will be calculated for all individual derived PK parameters including exposure information of decitabine.

All plasma concentrations below the lowest quantifiable concentration or missing data will be labeled as such in the concentration data presentations or SAS dataset. Concentrations below the lower quantifiable concentration will be treated as zero in the summary statistics. All subjects and samples excluded from the analysis will be clearly documented in the Clinical Study Report.

Descriptive statistics will be used to summarize decitabine serum concentrations at each sampling time point and PK parameters of decitabine:  $C_{\min}$  and  $C_{\max}$ . Other PK parameters, including but not limited to  $AUC_{(t1-t2)}$ ,  $t_{1/2}$ , CL, and V, when available, will also be summarized.

## **11.6. Pharmacokinetic/Pharmacodynamic Analyses**

The relationship between decitabine plasma concentrations and/or metrics of systemic exposure ( $C_{\max}$ , AUC) with markers of pharmacological activities (DNA methylation status, gene expression profiles) will be explored using suitable structural models and non-linear mixed effect regression techniques.

## **11.7. Biomarker Analyses**

Biomarker analyses will be performed and stratified by clinical covariates or molecular subgroups using appropriate statistical methods. When too few data are available for statistical analyses, data will be summarized with descriptive statistics and/or visualized.

Pharmacodynamic biomarker results from Phase 1 and 2 will be summarized with descriptive statistics and/or visualized for each dose level. Changes in the values of individual biomarkers from baseline to selected time points will be summarized by dose cohort.

Correlation of baseline values or changes in biomarker values with response or time-to-event endpoints will identify responsive (or resistant) subgroups of patients as well as genes and pathways affected by DACOGEN treatment.

Planned biomarker analyses are dependent upon the availability of appropriate biomarker assays and may be deferred if emerging study data show no likelihood of providing useful scientific information.

Results of biomarker analyses will be presented in a separate report.

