- k) Bone marrow aspirates will be performed at the end of Cycle 1 of sequential treatment (Day 28 or within 8 days of the start of the next cycle), the end of Cycle 2 if the subject did not achieve a CR at the end on Cycle 1, at the end of sequential treatment, or at any time disease progression is suspected. For Phase 1, bone marrow aspirates at end of Cycle 1 should be obtained no later than Day 42 in order to determine potential dose limiting toxicity. If available, a portion of the bone marrow aspirate collected at Screening and at end of the first Cycle will be used for DNA methylation/ mutation assessment, gene expression, and micro RNA analyses.
- l) Results should be recorded if a bone marrow aspirate is obtained as part of standard clinical care.

- m) Response assessment is performed at time at which bone marrow aspirate is obtained.
- n) Hemoglobin, platelet count, white blood cell count, absolute neutrophil count (ANC), peripheral blast count
- o) First cycle only
- p) For the DACOGEN continuation period, hematology samples are obtained on Day 1 of each cycle prior to drug administration.
- q) To include  $\text{Na}^+$ ,  $\text{K}^+$ , creatinine, aspartate aminotransferase (AST), alanine aminotransferase (ALT), total bilirubin, serum uric acid
- r) 0.5 mL whole blood to be obtained (blood should not be collected through the same line through which decitabine is infused, see Section 9.2.3) at; pre-infusion, 0.5 h during infusion, end of infusion, +5 min, +0.5h, +1h, and +2h after end infusion. Samples will be collected from Phase 1 and Phase 2 subjects. 0.5 ml of cerebrospinal fluid (CSF) will be collected for PK analysis when/if CSF is obtained as part of routine medical care except at screening.
- s) Whole blood sample (2 mL) for DNA methylation pattern and DNA mutation determination at screening, prior to drug administration on Day, 8, and at the end of Cycle 1. This sample may also be used for gene expression and micro RNA analysis in the event only one biomarker blood sample can be drawn.
- t) Whole blood (2.5 mL) for gene expression profiling and micro RNA analysis at screening, prior to drug administration on Day 8, and at the end of Cycle 1.

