### 6.3. Dosage and Administration

DACOGEN will be administered as a 1-hour IV infusion of 20 mg/m^2 once daily for 5 consecutive days on Days 1 to 5 of each 28 day cycle. Cytarabine will be administered as an IV infusion over 4 hours daily for 5 consecutive days (Day 8 to Day 12). The DACOGEN dose is considered the biologically active dose based on studies of DNA hypomethylation in adults and is far below (1/20th) the MTD for single-agent decitabine determined in children and adults. The amounts of both agents are determined by body surface area calculations.

The dose should be recalculated if the subject's body surface area (BSA) changes by more than 10%. For subjects who are less than 1 year old, or have a body weight of less than 10 kg, the assigned doses of DACOGEN and cytarabine should be based on the subject's body weight. This conversion is calculated as dose described by BSA in mg/m^2 divided by 30 and multiplied by body weight (kg).

The MTD of cytarabine will be determined in the Phase 1 portion of the study. The starting dose of cytarabine will be 1 g/m^2 per day x 5 days and the second dose level will be 2 g/m^2 per day x 5 days. If the first dose level is not tolerated the study will stop since cytarabine 1 g/m^2 per day x 5 days is the lowest dose generally used in this setting. If the first dose level is tolerated but the second dose level exceeds the MTD, an intermediate dose level, 1.5 g/m^2 per day x 5 days will be evaluated.

In the Phase 1 portion, dose limiting toxicity (DLT) will be assessed for each subject who receives at least 1 cycle of the sequential DACOGEN - cytarabine treatment. Subjects will be enrolled into Phase 1 using a “rolling 6” design. A minimum of 2 subjects and up to 6 subjects will be continuously enrolled at each dose level. Enrollment suspension for each dose level may occur only when 6 subjects have been enrolled.

**Table 3** depicts the decision making algorithm for the determination of the appropriate dose level of cytarabine for the next enrolled subject, enrollment suspension, MTD determination, or study termination.

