### 6.3.1. Dose Delays

Cycles may be delayed up to 28 days to allow for recovery from toxicity. Subjects with bone marrow aplasia/hypoplasia (defined as overall marrow cellularity less than 25%) or absolute neutrophil count (ANC)  $<0.5 \times 10^9/L$  or non-transfusion dependent platelet count  $<25 \times 10^9/L$  should not start their next cycle until further hematopoietic recovery. The DACOGEN dose will be held constant but the cytarabine dose may be adjusted for toxicity.

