##### **Dose Limiting Toxicity (DLT) for Cytarabine**

For the Phase 1 portion of the study the primary endpoint will be DLT in the determination of the MTD (up to 2 g/m^2 per day) of cytarabine given on Days 8 to 12 following the administration of DACOGEN at 20 mg/m^2 on Days 1 to 5. DLTs are defined as the following

- Hematological DLT will be defined as failure to recover to an absolute neutrophil count (ANC) of  $0.5 \times 10^9/L$  (common terminology criteria for adverse events [CTCAE] Grade 3) and non-transfusion dependent platelet count of  $25 \times 10^9/L$  (CTCAE Grade 3) due to documented bone marrow aplasia/hypoplasia (malignant infiltration or other cause excluded), by Day 42. Bone marrow aplasia/hypoplasia is defined as overall marrow cellularity less than 25%.
- Non-hematological DLT is defined as: any Grade  $\geq 3$  toxicity possibly, probably or definitely related to study drug that persists for  $>5$  days; any Grade 2 toxicity that persists for  $>7$  days and that is intolerable to the patient.

The following events are more likely disease-related and, therefore, not considered DLTs:

- Grade 3 or 4 disseminated intravascular coagulation
- Grade 3 tumor lysis syndrome; grade 3 or 4 fever or grade 3 catheter-related infection, febrile neutropenia, infection, infection with unknown neutrophil count, and infection without neutropenia
- Grade 3 or 4 hypokalemia, hypomagnesemia, hyponatremia, or hypophosphatemia that is related to AML or administration of antifungal medications and is corrected with IV or oral supplementation.

Subjects who do not complete one treatment cycle and do not develop DLT will not be considered evaluable for DLT.

Decitabine PK parameters including  $C_{max}$ , AUC,  $t_{max}$ , and Cl will be determined from blood sampling on Day 5 of Cycle 1 and are a primary endpoint for the Phase 1 portion of the study.

#### Phase 2

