### 9.2.5. Pharmacokinetic Parameters

PK analysis will be the responsibility of the Sponsor in accordance with the sponsor's current Clinical Pharmacokinetics Guideline. The following PK parameters for decitabine will be calculated on Day 5 of Cycle 1 by non-compartmental methods using WinNonlin Version 5.0 or higher:

$C_{max}$	maximum plasma concentration
$t_{max}$	time to reach the maximum plasma concentration
$AUC_{last}$	area under the plasma concentration-time curve from time 0 to the time of the last quantifiable concentration
$AUC_{\tau}$	area under the plasma concentration-time curve from time 0 to 24 hr
$t_{1/2, \lambda}$	elimination half-life associated with the terminal slope ( $\lambda_z$ ) of the semilogarithmic drug concentration-time curve, calculated as $0.693/\lambda_z$
$\lambda_z$	first-order rate constant associated with the terminal portion of the curve, determined as the negative slope of the terminal log-linear phase of the drug concentration-time curve
CL	total clearance of drug after IV administration, calculated as: dose/ $AUC_{\tau}$
$VD_{ss}$	volume of distribution at steady state, calculated as $\lambda_z / CL$

Actual blood sampling times relative to study medication administration will be used for the analysis. Additional PK parameters may be determined as appropriate.

Cytarabine PK parameters will not be evaluated. They are already well described in this population at the doses planned. Since decitabine has a terminal half-life of  $0.51 \pm 0.31$  hour (DACOGEN package insert) and two full days will pass from the last dose of decitabine to the first of cytarabine, no drug-drug interaction is expected.

Based on the individual plasma concentration-time data, using the actual dose taken and the actual sampling times, pharmacokinetic parameters and exposure information of decitabine will be derived using population pharmacokinetic modeling. Baseline covariates (eg, body weight, age, sex, creatinine clearance, race) may be included in the model, if relevant.

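### Section 11.7 splits the Day 8 biomarker change by cytarabine dose cohort although no cytarabine has yet been given; a summary pooled over cytarabine levels would be more precise at no cost

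*Combined protocol and SAP*

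**What the plan says.** **Treatment.** Under Section 6.3 every subject receives DACOGEN 20 mg/m² on Days 1 to 5, and cytarabine starts a week into the cycle: "Cytarabine will be administered as an IV infusion over 4 hours daily for 5 consecutive days (Day 8 to Day 12"). Section 6.3.1 confirms which drug's dose can vary: "The DACOGEN dose will be held constant but the cytarabine dose may be adjusted for toxicity".

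**Sampling.** Decitabine PK is drawn on Cycle 1 Day 5. Blood for DNA methylation and mutation is drawn "at screening, prior to drug administration on Day, 8, and at the end of Cycle 1" (Time and Events Schedule, footnote s). Footnote t gives the same three times for gene expression and microRNA.

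**Biomarker summaries.** Section 11.7 gives pharmacodynamic results from both phases separately for each dose level, and adds: "Changes in the values of individual biomarkers from baseline to selected time points will be summarized by dose cohort". The time points are not named, and Day 8 is not treated differently from the end of Cycle 1.

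**PK summaries.** Section 11.5 first states: "For each treatment group, descriptive statistics, including arithmetic mean, SD, coefficient of variation, median, minimum, and maximum will be calculated". Its last paragraph then summarises concentrations and PK parameters without naming any grouping. It also plans a population PK model that is not described as split by group.

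**The concern.** Grouping by dose is useful where dose can act. At Day 8 it cannot: all subjects have had the same nominal DACOGEN regimen and no study cytarabine. The Day 8 change from baseline is therefore the plan's cleanest view of DACOGEN's own pharmacodynamic effect, which Section 2.1 lists among the objectives. Reporting it only by cytarabine cohort divides a small sample on a factor that is irrelevant at that time. Each cohort mean is then less precise than it need be, and a reader may take chance differences between cohorts for a dose effect.

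The split that the protocol does name as of interest is age: Section 3.2 allows pharmacodynamic analyses across age groups, and Section 9.4.1 wants biological activity shown over all ages enrolled.

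**Working it through.** **1. What the dose terms mean.** DACOGEN is fixed at 20 mg/m². The only dose that differs between cohorts is cytarabine, at 1.0, 1.5 or 2.0 g/m² per day. The dose level and dose cohort of 11.7 are therefore cytarabine levels.

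**2. Which samples precede cytarabine.**
- Screening blood is the baseline.
- Day 5 PK precedes cytarabine. Section 9.2.5 says so itself: "two full days will pass from the last dose of decitabine to the first of cytarabine".
- Day 8 blood, before that day's drug, precedes cytarabine.
- End-of-Cycle-1 blood follows cytarabine, so the cohort split is sensible there.

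Of the two changes from baseline, only the one to Day 8 is affected.

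**3. Sizes, from the plan.** Section 6.3 sets 2 to 6 subjects per level. Section 11.2 gives a Phase 1 maximum of 12 evaluable subjects, or 18 with the intermediate level. Both reproduce: 2 × 6 = 12 and 3 × 6 = 18. The same section puts at least 15 evaluable subjects at the MTD by the end of Phase 2, counting Phase 1 subjects treated at that dose.

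**4. Precision lost.** With the same between-subject variance in each cohort, the standard error of a mean is SD/√n. The ratio of cohort to pooled standard error is √(N pooled / n cohort), whatever the SD.

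| Cohort n | Pooled N | Ratio |
|---|---|---|
| 6 | 12 (Phase 1, two levels) | √2 = 1.41 |
| 6 | 18 (Phase 1, three levels) | √3 = 1.73 |
| 15 (MTD) | 15 + 3 = 18 | √(18/15) = 1.10 |
| 15 (MTD) | 15 + 6 = 21 | √(21/15) = 1.18 |
| 15 (MTD) | 15 + 12 = 27 | √(27/15) = 1.34 |

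The figure of 27 needs all three levels to fill with 6 subjects: 12 away from the MTD, and 6 already counted in the 15. The table assumes that each counted subject gives a usable Day 8 sample. Section 9.6 ranks biomarker blood third and fourth in priority, so real numbers may be smaller.

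**5. Illustration for PK only.** Section 1.1.4.1 gives a CV of about 50% for decitabine clearance in cancer subjects. Using it for children is an assumption, so 30% and 70% are shown as well. The 95% half-width as a share of the mean is t(0.975, n−1) × CV/√n.
- CV 50%, n = 6: 2.571 × 0.5/√6 = 52.5%; n = 18: 2.110 × 0.5/√18 = 24.9%.
- CV 50%, n = 15: 2.145 × 0.5/√15 = 27.7%; n = 27: 2.056 × 0.5/√27 = 19.8%.
- CV 30%, n = 6 against 18: 31.5% against 14.9%.
- CV 70%, n = 6 against 18: 73.5% against 34.8%.

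The plan computes no such intervals for PK or biomarkers, and it gives no biomarker variability. These figures show scale only.

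**The case against.** **These are descriptive, exploratory tables.** Section 11.7 attaches no test, interval or precision target to them and sends the results to a separate report. It already allows stratification by clinical covariates or molecular subgroups, and Section 11 leaves specifics to the statistical analysis plan. Nothing forbids a pooled row. All of this stands, and it is why the point is minor. The grouping that is written down is still the less informative one for Day 8.

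**A cohort view of Day 8 has some use.** It lets a reader follow each cohort from screening through Day 8 to the end of Cycle 1. That justifies a supporting display, but not making it the only summary.

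**Subjects are not interchangeable.** Ages run from 1 month to under 18 years, and dosing is by weight below 1 year or 10 kg. This is correct, but it argues for looking by age, not by cytarabine level.

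**A stronger reading is tempting.** Decitabine PK parameters "will be determined from blood sampling on Day 5 of Cycle 1 and are a primary endpoint for the Phase 1 portion", and 11.5 groups one PK summary, so a reader might infer that precision is lost on a Phase 1 primary endpoint. The documents do not support that. The term treatment group is undefined in this single-arm study; it may mean one group, a phase or a cytarabine level. The last paragraph of 11.5 names no grouping. The population PK model is not split, so it draws on all subjects with usable data. What remains for PK is an ambiguity in 11.5.

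**Conclusion.** The point holds for the Day 8 biomarker change from baseline. Section 11.7 groups it by a factor that cannot yet have acted. The per-cohort standard error is about 1.7 times the pooled one for 6 against 18 subjects. For an MTD cohort of 15 it is about 1.1 to 1.3 times, depending on how many subjects were treated at other levels. These ratios rest on equal variance across cohorts and complete Day 8 sampling; they need no assumed CV.

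For Day 5 PK the finding is narrower: 11.5 uses an undefined grouping term, and one of its PK summaries is grouped while another is not. No dose decision, MTD determination or response analysis is affected. This is a minor, free improvement.

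**What to change.** - **Section 11.7:** make the main summary of the Day 8 change from baseline pooled over cytarabine levels and both phases, with a breakdown by age group if numbers allow. Keep dose-cohort summaries for the end-of-Cycle-1 sample, and show Day 8 by cohort, if at all, only as supporting context. Name the time points.
- **Section 11.5:** define treatment group, or drop the term, and state that Day 5 decitabine PK parameters are summarised pooled over cytarabine levels. Bring the grouped and ungrouped paragraphs into line.

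The cost is a few lines of wording and table shells, with no new data, samples or subjects.
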